6.6.3 Laboratory data

Clinical laboratory values will be expressed in Standard International (SI) units. Laboratory data collected and recorded as below the limit of detection will be set equal to the lower limit of detection for the calculation of summary statistics.

Summary data for each laboratory parameter will be presented for each continuous clinical laboratory parameter (including hematology, serum chemistry, coagulation studies and thyroid and liver function tests). Descriptive statistics will be presented for the actual values, change from baseline, and percent change from baseline by visit.

For each continuous laboratory parameter, results will be categorized as low, normal, or high based on the laboratory normal ranges.

A listing will be produced for all patients with abnormal liver function tests defined as an ALT $>3\times\text{ULN}$, AST $>3\times\text{ULN}$, and/or total bilirubin $>2\times\text{ULN}$ at any time point.

A table will be produced to summarize the number and percentage of patients in each of below category at any post-baseline time point.

- ALT >1 & ≤ 3 , >3 & ≤ 5 , >5 & ≤ 10 , >10 & ≤ 20 , $>20\times\text{ULN}$,
- AST >1 & ≤ 3 , >3 & ≤ 5 , >5 & ≤ 10 , >10 & ≤ 20 , $>20\times\text{ULN}$,
- ALT or AST >1 & ≤ 3 , >3 & ≤ 5 , >5 & ≤ 10 , >10 & ≤ 20 , $>20\times\text{ULN}$,
- ALP $>1.5\times\text{ULN}$,
- Total Bilirubin >1.5 & ≤ 2 , >2 & ≤ 3 , >3 & ≤ 5 and $>5\times\text{ULN}$,
- Total Bilirubin $>2\times\text{ULN}$ concurrent with ALT or AST $>3\times\text{ULN}$,
- INR >1.2 .

In separate figures, the peak total bilirubin (at any time post-baseline) will be plotted against the peak AST, the peak ALT, and the peak AST or ALT levels at any time post-baseline.

For hematology and blood chemistry, summary tables of potentially clinically significant abnormalities (PCSA) will be provided.

Laboratory data will be provided in data listings as appropriate. Values met PCSA criterion or out-of-range laboratory results when no PCSA criterion is defined will be identified in the listings.

6.6.4 Vital signs and physical examination

Descriptive statistics will be provided for vital signs, including blood pressure, pulse rate, oral body temperature and respiration rate. Summary table of potentially clinically significant abnormalities (PCSA) will be provided.

Vital sign measurements will be presented for each patient in a data listing as appropriate, with PCSA vital signs flagged.

All physical examination findings will be presented in a by-patient data listing.

6.6.5 Electrocardiogram

Electrocardiogram (ECG) findings will include rhythm, ventricular rate, PR interval, QRS duration, QT interval, and QTc interval. For post-baseline assessments where ECG is performed in triplicate, the average of the 3 (or all available) readings will be used for analysis.

Corrected QT interval (QTc), if not collected, will be calculated using both Bazett's and Fridericia's correction formulas.

PR, QRS, QT, QTc and RR intervals and their change from time-matched and pre-dose baseline will be summarized for each treatment group by scheduled visit. Patients will be categorized into ≤ 450 , $>450 - 480$, $>480 - 500$, or >500 ms per their maximum post-baseline absolute QTc interval and ≤ 30 , $>30 - 60$, or >60 ms per their maximum change from baseline QTc interval. The number and percentage of patients in each category will be summarized by treatment group.

6.6.6 Medical history

Medical history will be summarized by MedDRA coding system (version 18.0 or later) SOC, high level term (HLT), and PT. A patient contributes only once to the count for a given condition (overall, by SOC, by HLT, by preferred term). Listing will be provided including medical condition or event, start date and end date.

6.6.7 Concomitant medications

Concomitant medication is defined as all medications other than study drug administered to a patient with the medication taken after first fitusiran dose for fitusiran arm or after Day 1 visit for the on-demand arm.

Concomitant medications will be coded using the WHO Drug Dictionary (version in use at the time of database lock). Results will be tabulated by anatomic therapeutic class (ATC) and preferred term.

Concomitant medications collected will be tabulated by treatment arm and summarized separately for the bleeding treatment medications (as captured in the eDiary) and other medications (as captured in the CRF). Any medications that did not end prior to first fitusiran dose for fitusiran arm or prior to Day 1 visit for on-demand arm will be included. If an end date is missing or the medication is ongoing, the medication will be included.

6.7 Anti-drug antibody analysis

The ADA population includes all patients in the safety analysis set with at least one post baseline ADA result. Number of patients testing positive for ADA pre-study-drug (baseline positive) and post-study-drug administration will be summarized by Hemophilia type (A/B) and incidence of ADA positivity will be presented by frequency and as a percent by Hemophilia type and across all patients. In addition, maximum ADA titer and range of titer values will be presented by Hemophilia type and across all patients.

8 APPENDICES

8.1 Questionnaire/Scoring

8.1.1 Haem-A-QOL and Haemo-QOL

The Haem-A-QOL and Haemo-QOL questionnaires are psychometrically tested QOL assessment instruments for patients with hemophilia.

The Haem-A-QOL will be provided to patients ≥ 17 years of age, and includes 46 items contributing to 10 QOL domains (physical health, feelings, view of yourself, sports and leisure, work and school, dealing with hemophilia, treatment, future, family planning, partnership and sexuality). Scoring for each item is based on a 5-point Likert scale (never, rarely, sometimes, often, and all the time), and higher scores represent greater impairment.

8.1.2 Treatment satisfaction questionnaire for medication (TSQM) domain scores

The Treatment Satisfaction Questionnaire for Medication (TSQM) will assess patient satisfaction with treatment. The TSQM is a validated psychometric tool that provides a general measure of patient satisfaction with medication.

The TSQM Scale scores will be computed by adding the items loading on each factor. The lowest possible score is subtracted from this composite score and divided by the greatest possible score minus the lowest possible score. This provides a transformed score between 0 and 1 that should be multiplied by 100; see [Table 2](#). Note that only one item may be missing from each scale before the subscale should be considered invalid for that respondent.

Table 2 - TSQM scale scores

Factor	Calculation	In case of missings
Effectiveness	$[(\text{Item 1} + \text{Item 2} + \text{Item 3}) - 3] \text{ divided by } 18) * 100$	If one item is missing: $[(\text{Sum}(\text{Item 1?} + \text{Item 2?} + \text{Item 3?})) - 2] \text{ divided by } 12) * 100$
Convenience	$[(\text{Sum}(\text{Item 4 to Item 6}) - 3) \text{ divided by } 18) * 100$	If one item is missing: $[(\text{Sum}(\text{Item4? to Item6?})) - 2] \text{ divided by } 12) * 100$
Global Satisfaction	$[(\text{Sum}(\text{Item 7 to Item 9}) - 3) \text{ divided by } 14) * 100$	If either Item 7 or 8 is missing: $[(\text{Sum}(\text{Item7? to Item9?})) - 2] \text{ divided by } 10) * 100$ If Item 9 is missing: $[(\text{Sum}(\text{Item7 and Item8})) - 2] \text{ divided by } 8) * 100$

8.1.3 Haemophilia activities list (HAL)/paediatric HAL (pedHAL) score

The HAL and pedHAL questionnaires will assess subjective functional ability to perform activities of daily living. The HAL will be assessed in patients ≥ 18 years of age, and the pedHAL will be assessed in patients < 18 years of age.

HAL scores can be calculated for each of the seven domains of the HAL. Additionally, three component scores can be calculated (Activities involving the Upper Extremities, Basic activities involving the Lower Extremities and Complex activities involving the Lower Extremities) as well as an overall score. If there is missing item score within a domain or a component, the normalized score for that domain or component will be calculated based on the number of items answered if at least 50% of those scores are non-missing and otherwise it is set to missing. Before summarizing the individual item scores, recoding is required (see [Table 3](#)); a higher raw score represents more functional limitations; possible scoring ranges are given ([Table 4](#)). Normalized scores for the domains, components, and the full questionnaire can also be obtained. Missing values are controlled for and the possible scores range from 0 to 100, where 0 represents the worst possible functional status and 100 the best possible functional status ([Table 5](#)).

Table 3 - Recoding

Score	Recode	Meaning
8	0	N/A
1	6	Impossible
2	5	Always problems
3	4	Mostly problems
4	3	Sometimes problems
5	2	Rarely problems
6	1	Never problems

Table 4 - Scores

Score		Items	Score range
Lying/sitting/kneeling/standing	LSKS	1-8 (8)	8 - 48
Functions of the legs	LEGS	9-17 (9)	9 - 54
Functions of the arms	ARMS	18-21 (4)	4 - 24
Use of transportation	TRANS	22-24 (3)	3 - 18
Self care	SELFC	25-29 (5)	5 - 30
Household tasks	HOUSEH	30-35 (6)	6 - 36
Leisure activities and sports	LEISPO	36-42 (7)	7 - 42
Upper Extremity Activities	UPPER *	(9)	9 - 54
Basic Lower Extremity Activities	LOWBAS **	(6)	6 - 36
Complex Lower Extremity Activities	LOWCOM ***	(9)	9 - 54
Sum score	SUM 1-42	(42)	42 - 252

* Items for UPPER-component: 18, 19, 20, 21, 25, 26, 27, 28, 29. (9 items)

** Items for LOWBAS-component: 8, 9, 10, 11, 12, 13. (6 items)

*** Items for LOWCOM-component: 3, 4, 6, 7, 14, 15, 16, 17, 22. (9 items)

Table 5 - Normalization

Score	Normalisation
LSKS	$100 - ((\Sigma 1-8 - \text{valid}) * (100/(5 * \text{valid})))$
LEGS	$100 - ((\Sigma 9-17 - \text{valid}) * (100/(5 * \text{valid})))$
ARMS	$100 - ((\Sigma 18-21 - \text{valid}) * (100/(5 * \text{valid})))$
TRANS	$100 - ((\Sigma 22-24 - \text{valid}) * (100/(5 * \text{valid})))$
SELFC	$100 - ((\Sigma 25-29 - \text{valid}) * (100/(5 * \text{valid})))$
HOUSEH	$100 - ((\Sigma 30-35 - \text{valid}) * (100/(5 * \text{valid})))$
LEISPO	$100 - ((\Sigma 36-42 - \text{valid}) * (100/(5 * \text{valid})))$
UPPER	$100 - ((\Sigma 18-21; 25-29 - \text{valid}) * (100/(5 * \text{valid})))$
LOWBAS	$100 - ((\Sigma 8-13 - \text{valid}) * (100/(5 * \text{valid})))$
LOWCOM	$100 - ((\Sigma 3-7; 14-17; 22 - \text{valid}) * (100/(5 * \text{valid})))$
SUM	$100 - ((\Sigma 1-42 - \text{valid}) * (100/(5 * \text{valid})))$

"valid" = number of items scored within the specific domain/component.

Items with "n/a"-response are to be considered NOT valid

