6.3.3.2 HAL and pedHAL

The Haemophilia Activities List (HAL, in patients ≥ 18 years of age) and pediatric HAL (pedHAL, in patients < 18 years of age) questionnaires assess subjective functional ability to perform activities of daily living. Overall score, component scores, domain scores, and their changes will be summarized by scheduled visits.

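### For the HAL complex lower-extremity component, SAP Table 5 sums ten items including item 5, while SAP Table 4 defines nine items without it

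*SAP*

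**What the plan says.** SAP section 8.1.3 scores the HAL in three steps. Item responses are recoded to 1 (never problems) through 6 (impossible), with N/A recoded to 0, so that "a higher raw score represents more functional limitations". SAP Table 4 gives the items and raw range of each score. SAP Table 5 gives the formula that converts the raw sum to a normalised score.

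For the component labelled "Complex Lower Extremity Activities", the Table 4 row gives nine items and a raw range of 9 to 54. The footnote lists them: "Items for LOWCOM-component: 3, 4, 6, 7, 14, 15, 16, 17, 22. (9 items". Item 5 is not among them. The Table 5 row for the same component sums items 3 to 7, 14 to 17 and 22, which does include item 5.

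The note under Table 5 defines *valid* as the "number of items scored within the specific domain/component" and adds: "Items with 'n/a'-response are to be considered NOT valid". A domain or component score "will be calculated based on the number of items answered if at least 50% of those scores are non-missing". The text says that "the possible scores range from 0 to 100, where 0 represents the worst possible functional status and 100 the best possible functional status".

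The planned use is in SAP section 6.3.3.2: "Overall score, component scores, domain scores, and their changes will be summarized by scheduled visits".

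**The concern.** One appendix section gives two item sets for one score. A programmer is likely to work from Table 5, because it holds the formula, and would then bring in an item that Table 4 leaves out. The SAP does not say which table prevails, and no other section of either document settles it. Two programmers following the same SAP could report different LOWCOM values, which defeats the purpose of a scoring appendix.

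At stake are the LOWCOM score and its change from baseline, both planned outputs for an exploratory endpoint. One form of the error would show up as negative scores. The other stays in range, so a range check would not find it.

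**Working it through.** **Inputs (SAP 8.1.3).** Recoded items run from 1 to 6. Table 4 LOWCOM items: 3, 4, 6, 7, 14, 15, 16, 17, 22 (nine). Table 5 LOWCOM sum: 3, 4, 5, 6, 7, 14, 15, 16, 17, 22 (ten). With raw sum S and valid count v, the Table 5 formula is

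score = 100 - (S - v) × 100 / (5v).

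**The plan's own figures, using the nine Table 4 items throughout.** The raw range is 9 × 1 = 9 to 9 × 6 = 54, as Table 4 states. The best score is 100 - (9 - 9) × 100/45 = 100. The worst is 100 - (54 - 9) × 100/45 = 0. Both match the text.

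**The other rows.** Comparing the item sets of Tables 4 and 5 for all eleven scores, the other ten agree and give exactly 0 to 100. LOWCOM is the only mismatch, and item 5 is the only extra item.

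**Reading A: ten-item sum, v = 9** (the Table 5 note taken literally, with the component as Table 4 defines it), all nine items and item 5 answered.

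- All items best: S = 10, score = 100 - (10 - 9) × 100/45 = 97.8.
- All items worst: S = 60, score = 100 - (60 - 9) × 100/45 = -13.3.
- In general, if item 5 has recoded value x, the score is lower than the nine-item score by x × 100/45. For x = 1 to 6 this is 2.2, 4.4, 6.7, 8.9, 11.1 and 13.3 points.
- With missing items the shift grows. If only five of the nine are answered (5/9 = 56%, allowed by the 50% rule) plus item 5, then v = 5. The range is 100 - (36 - 5) × 100/25 = -24.0 to 100 - (6 - 5) × 100/25 = 96.0.

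**Reading B: ten-item sum, v = 10,** all ten answered.

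- Best: S = 10, score = 100. Worst: S = 60, score = 100 - (60 - 10) × 100/50 = 0. The range is respected.
- Let m be the mean of the nine component items. The nine-item score is 120 - 20m. The ten-item score is 100 - 2(9m + x - 10) = 120 - 18m - 2x. The difference (ten-item minus nine-item) is 2(m - x).
- It is zero when item 5 equals the mean of the other nine. The extremes are nine items best with item 5 worst (90 instead of 100) and the reverse (10 instead of 0), so at most 10 points.

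**Item 5 N/A.** It adds 0 to the sum and is not valid, so both readings return the nine-item score.

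**One patient, three scores.** Nine items recoded 2 and item 5 recoded 6: nine-item score 100 - (18 - 9) × 100/45 = 80.0; reading A 100 - (24 - 9) × 100/45 = 66.7; reading B 100 - (24 - 10) × 100/50 = 72.0. This is a deliberately discordant patient. With item 5 recoded 3, reading B gives 100 - (21 - 10) × 100/50 = 78.0.

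**Change from baseline.** Under reading A, each one-level change in item 5 moves the score by 100/45 = 2.2 points, up to 5 × 100/45 = 11.1. The offset cancels if item 5 and the number of valid items do not change. Under reading B, a one-level change in a true component item counts 100/50 = 2.0 points instead of 2.2, and item 5 counts 2.0.

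**The case against.** The strongest reply is that the out-of-range result needs a mixture: summing by Table 5 and counting by Table 4. A program that uses one item list for both stays within 0 to 100. That is right as far as it goes. But the mixture is what the note under Table 5 literally prescribes, and a program using the Table 5 list for both still scores a component other than the one defined.

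A reader might also infer more than the documents support:

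- *That LOWCOM scores leave 0 to 100 whichever way they are programmed.* This happens only with v = 9, and only below 0, never above 100.
- *That the score is wrong for every patient who answers item 5.* This holds with v = 9. With v = 10 it does not: a fully able patient still scores 100, a fully limited patient 0, and anyone whose item 5 equals the mean of the other nine is unaffected.
- *That the HAL results or the trial's efficacy conclusions are in doubt.* The HAL is exploratory, section 6.3.3.2 plans only summaries, and it is outside the testing hierarchy in SAP section 5.7. The seven domain scores, the other two component scores and the overall score are consistent between the tables. The same formula would apply to both arms, and no effect on the arm comparison has been shown.

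Finally, the instrument's scoring manual is not among the documents, so Table 4 cannot be proved right from them. This stands as a caution. The item list, the count, the raw range and the 0 to 100 statement all fit nine items, and the Table 5 row fits none of them under the literal count. The row is otherwise well formed, and the UPPER row, which joins ranges in the same way, is correct. A shorthand slip of 3-7 for 3-4; 6-7 is the likeliest explanation.

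**Conclusion.** The contradiction is certain: nine items without item 5 in SAP Table 4, ten with it in SAP Table 5. Its numerical effect is conditional. With *valid* counted over the nine component items, and all nine plus item 5 answered, scores are 2.2 to 13.3 points too low and run from -13.3 to 97.8. With *valid* counted over ten items, all answered, scores stay in range and differ from the nine-item score by 0 to 10 points in either direction. The effect is nil if item 5 is N/A.

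Severity is minor. One descriptive, exploratory component score is affected; the HAL domain scores, the overall HAL score, and the primary and secondary endpoints are not. Treating the nine-item version as the reference rests on its agreement with the rest of section 8.1.3, not on the scoring manual.

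**What to change.** Confirm the LOWCOM item list against the instrument's scoring manual. If it agrees with SAP Table 4, change the Table 5 LOWCOM sum to items 3-4; 6-7; 14-17; 22 and state that *valid* is counted over those nine items. This restores a raw range of 9 to 54 and a normalised range of 0 to 100. If the manual instead includes item 5, the Table 4 row, its footnote and the raw range must change to match.

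Then check the scoring program for the items in the sum, the items in the count, and the items used for the 50% rule. A test record with nine items recoded 2 and item 5 recoded 6 separates the three versions: 80.0, 66.7 or 72.0.

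The cost is one line in an SAP appendix and a short program check. No new data are needed, and no other analysis changes.

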8.1.4 EuroQol-5 dimension 5 level (EQ-5D-5L) score

The EQ-5D-5L is a standardized instrument for use as a measure of QoL outcome. It consists of a descriptive system and a visual analog scale (VAS).

- 1) EQ-5D descriptive system: has 5 dimensions (mobility, self-care, usual activities, pain/discomfort, anxiety/depression) with 5 levels (no problems, slight problems, moderate problems, severe problems, and extreme problems).
- 2) EQ-5D VAS: is a continuous score ranging from 0 to 100.
- 3) EQ-5D Valuation index: The information of the 5 dimensions of the descriptive system summarized into one index. The EQ-5D-5L index value is calculated using the crosswalk link function and the individual responses to the EQ-5D5L descriptive system. If any of the 5 dimensions have missing values at a given time point, the index value will not be computed.

8.2 List of search terms for COVID-19 (MedDRA v23.0)

Code	PT	Primary SOC
10084510	N/A	Infections and infestations
10084459	Asymptomatic COVID-19	Infections and infestations
10084467	Asymptomatic COVID-19	Infections and infestations
10053983	Coronavirus infection	Infections and infestations
10051905	Coronavirus infection	Infections and infestations
10084382	COVID-19	Infections and infestations
10084268	COVID-19	Infections and infestations
10084401	COVID-19	Infections and infestations
10084270	COVID-19	Infections and infestations
10084272	COVID-19	Infections and infestations
10084381	COVID-19 pneumonia	Infections and infestations
10084380	COVID-19 pneumonia	Infections and infestations
10084383	COVID-19 pneumonia	Infections and infestations
10084451	Suspected COVID-19	Infections and infestations
10084452	Suspected COVID-19	Infections and infestations
10084461	SARS-CoV-2 carrier	Infections and infestations
10084456	Exposure to SARS-CoV-2	Injury, poisoning and procedural complications
10084394	Occupational exposure to SARS-CoV-2	Injury, poisoning and procedural complications
10084353	Coronavirus test	Investigations
10084269	Coronavirus test negative	Investigations
10070255	Coronavirus test positive	Investigations
10084508	SARS-CoV-2 test	Investigations
10084507	SARS-CoV-2 test	Investigations

10084500	SARS-CoV-2 test	Investigations
10084441	SARS-CoV-2 test	Investigations
10084499	SARS-CoV-2 test	Investigations
10084431	SARS-CoV-2 test	Investigations
10084356	SARS-CoV-2 test	Investigations
10084501	SARS-CoV-2 test	Investigations
10084493	SARS-CoV-2 test	Investigations
10084434	SARS-CoV-2 test	Investigations
10084440	SARS-CoV-2 test	Investigations
10084354	SARS-CoV-2 test	Investigations
10084481	SARS-CoV-2 test false negative	Investigations
10084480	SARS-CoV-2 test false negative	Investigations
10084495	SARS-CoV-2 test negative	Investigations
10084492	SARS-CoV-2 test negative	Investigations
10084504	SARS-CoV-2 test negative	Investigations
10084436	SARS-CoV-2 test negative	Investigations
10084502	SARS-CoV-2 test negative	Investigations
10084432	SARS-CoV-2 test negative	Investigations
10084357	SARS-CoV-2 test negative	Investigations
10084509	SARS-CoV-2 test negative	Investigations
10084494	SARS-CoV-2 test negative	Investigations
10084435	SARS-CoV-2 test negative	Investigations
10084438	SARS-CoV-2 test negative	Investigations
10084273	SARS-CoV-2 test negative	Investigations
10084505	SARS-CoV-2 test positive	Investigations
